9.2 Secondary Efficacy Endpoint(s)

- 1) Change from the baseline in the total score of PSP-rating scale after 12 weeks (3 months) of investigational product administration
- 2) Change from the baseline in the Montreal Cognitive Assessment - Korea (MoCA-K) after 12 weeks (3 months) and 24 weeks (6 months) of investigational product administration
- 3) Change from the baseline in the Korean Frontal Assessment Battery (K-FAB) after 12 weeks (3 months) and 24 weeks (6 months) of investigational product administration
- 4) Change from the baseline in the England & Schwab Activity of Daily Living (ES ADL) scale after 12 weeks (3 months) and 24 weeks (6 months) of investigational product administration
- 5) Change from the baseline in the score of each domain of the PSP-rating scale after 12 weeks (3 months) and 24 weeks (6 months) of investigational product administration
- 6) Change from the baseline in the score of each item of the PSP-rating scale after 12 weeks (3 months) and 24 weeks (6 months) of investigational product administration
- 7) Change from the baseline in the total score of modified PSP-rating scale 10 after 12 weeks (3 months) and 24 weeks (6 months) of investigational product administration
- 8) Change from the baseline in the total score of modified PSP-rating scale 14 after 12 weeks (3 months) and 24 weeks (6 months) of investigational product administration
- 9) Proportion of subjects with change from the baseline in the total score of PSP-rating scale ≤ 0 after 24 weeks (6 months) of investigational product administration [Subgroup: Richardson type]
- 10) Proportion of subjects with change from the baseline in the total score of Modified PSP-rating scale 10 ≤ 0 after 24 weeks (6 months) of investigational product administration [Subgroup: Richardson type]
- 11) Proportion of subjects with change from the baseline in the total score of Modified PSP-rating scale 14 ≤ 0 after 24 weeks (6 months) of investigational product administration [Subgroup: Richardson type]

9.2.1 Change from the baseline in the total score of PSP-rating scale after 12 weeks (3 months) of investigational product administration

9.2.1.1 Variable, Definition and/or Derivation

- Change from baseline at week 12 = week 12 – baseline

9.2.1.2 Method of Analysis

Descriptive statistics (number of subjects observed, mean, standard deviation, median, minimum, and maximum) will be presented by treatment group for each visit and the change from the baseline in the total score of the PSP-rating scale after 12 weeks (3 months) of investigational product administration. To test the difference between each study group and

the control group (GV1001 0.56 mg/day vs. control group, GV1001 1.12 mg/day vs. control group), an MMRM analysis will be conducted with the treatment groups, visits, and interactions between the visits and the treatment groups set as fixed effects, and the subjects set as the random effect, as well as considering the baseline values, age, and sex as covariates. The results of the MMRM analysis will be summarized by LSM and standard error (SE) for each treatment group, the LSM difference between treatment groups and its 95% confidence interval, and the two-sided p-value.

Additionally, testing the difference within each treatment group will be conducted by the same MMRM analysis.

MMRM constructed as follows

- Dependent Variable: Change from baseline in total score of PSP-rating
- Fixed Effects
 - Fixed Continuous Effects: Baseline PSP-rating, Age
 - Fixed Categorical Effects: Treatment, Visit, Visit*Treatment, Sex
- Repeated Effect: Visit
- Random Effect: Subject
- Covariance Structure: Unstructured (UN)

9.2.2 Change from the baseline in the Montreal Cognitive Assessment - Korea (MoCA-K) after 12 weeks (3 months) and 24 weeks (6 months) of investigational product administration

9.2.2.1 Variable, Definition and/or Derivation

- Change from baseline at week n = week n – baseline, n=12, 24

9.2.2.2 Method of Analysis

Descriptive statistics (number of subjects observed, mean, standard deviation, median, minimum, and maximum) will be presented by treatment group for each visit and the change from the baseline in MoCA-K after 12 weeks (3 months) and 24 weeks (6 months) of investigational product administration. To test the difference between each study group and the control group (GV1001 0.56 mg/day vs. control group, GV1001 1.12 mg/day vs. control group), an MMRM analysis will be conducted with the treatment groups, visits, and interactions between the visits and the treatment groups set as fixed effects, and the subjects set as the random effect, as well as considering the baseline values, age, and sex as covariates. The results of the MMRM analysis will be summarized by LSM and standard error (SE) for each treatment group, the LSM difference between treatment groups and its 95% confidence interval, and the two-sided p-value.

Additionally, testing the difference within each treatment group will be conducted by the same

MMRM analysis.

MMRM constructed as follows

- Dependent Variable: Change from baseline in MoCA-K
- Fixed Effects
 - Fixed Continuous Effects: Baseline MoCA-K, Age
 - Fixed Categorical Effects: Treatment, Visit, Visit*Treatment, Sex
- Repeated Effect: Visit
- Random Effect: Subject
- Covariance Structure: Unstructured (UN)

9.2.3 Change from the baseline in the Korean Frontal Assessment Battery (K-FAB) after 12 weeks (3 months) and 24 weeks (6 months) of investigational product administration

9.2.3.1 Variable, Definition and/or Derivation

- Change from baseline at week n = week n – baseline, n=12, 24

9.2.3.2 Method of Analysis

Refer to section 9.2.2.2.

9.2.4 Change from the baseline in the England & Schwab Activity of Daily Living (ES ADL) scale after 12 weeks (3 months) and 24 weeks (6 months) of investigational product administration

9.2.4.1 Variable, Definition and/or Derivation

- Change from baseline at week n = week n – baseline, n=12, 24

9.2.4.2 Method of Analysis

Refer to section 9.2.2.2.

9.2.5 Change from the baseline in the score of each domain of the PSP-rating

scale after 12 weeks (3 months) and 24 weeks (6 months) of investigational product administration

9.2.5.1 Variable, Definition and/or Derivation

- Change from baseline at week n = week n – baseline, n=12, 24

9.2.5.2 Method of Analysis

Refer to section 9.2.2.2.

9.2.6 Change from the baseline in the score of each item of the PSP-rating scale after 12 weeks (3 months) and 24 weeks (6 months) of investigational product administration

9.2.6.1 Variable, Definition and/or Derivation

- Change from baseline at week n = week n – baseline, n=12, 24

9.2.6.2 Method of Analysis

Refer to section 9.2.2.2.

9.2.7 Change from the baseline in the total score of modified PSP-rating scale 10 after 12 weeks (3 months) and 24 weeks (6 months) of investigational product administration

9.2.7.1 Variable, Definition and/or Derivation

- Change from baseline at week n = week n – baseline, n=12, 24

See Appendix 2 for calculation of the total score of modified PSP-rating scale 10.

9.2.7.2 Method of Analysis

Refer to section 9.2.2.2.

9.2.8 Change from the baseline in the total score of modified PSP-rating scale 14 after 12 weeks (3 months) and 24 weeks (6 months) of investigational product administration

9.2.8.1 Variable, Definition and/or Derivation

- Change from baseline at week n = week n – baseline, n=12, 24

See Appendix 2 for calculation of the total score of modified PSP-rating scale 14.

9.2.8.2 Method of Analysis

Refer to section 9.2.2.2.

9.2.9 Proportion of subjects with change from the baseline in the total score of PSP-rating scale ≤ 0 after 24 weeks (6 months) of investigational product administration [Subgroup: Richardson type]

9.2.9.1 Variable, Definition and/or Derivation

- Change from baseline at week n = week n – baseline, n=24
- Proportion of subjects with change ≤ 0 = the number of subjects with change ≤ 0 / the number of subjects with non-missing values x 100

9.2.9.2 Method of Analysis

Proportion of subjects with change from the baseline in the total score of PSP-rating scale ≤ 0 after 24 weeks and its two-sided 95% confidence interval will be provided by treatment group. To compare the study group and control group (GV1001 0.56 mg/day vs. control group, GV1001 1.12 mg/day vs. control group), p-value for the differences between groups will be provided using Pearson's chi-square test (if the cells with an expected frequency less than 5 does not exceed 20% of the total cells) or Fisher's exact test (if the cells with an expected frequency less than 5 exceed 20% of the total cells).

9.2.10 Proportion of subjects with change from the baseline in the total score of Modified PSP-rating scale $10 \leq 0$ after 24 weeks (6 months) of investigational product administration [Subgroup: Richardson type]

9.2.10.1 Variable, Definition and/or Derivation

- Change from baseline at week n = week n – baseline, n=24
- Proportion of subjects with change ≤ 0 = the number of subjects with change ≤ 0 / the number of subjects with non-missing values x 100

9.2.10.2 Method of Analysis

Refer to section 9.2.9.2.

9.2.11 Proportion of subjects with change from the baseline in the total score of Modified PSP-rating scale $14 \leq 0$ after 24 weeks (6 months) of investigational product administration [Subgroup: Richardson type]

9.2.11.1 Variable, Definition and/or Derivation

- Change from baseline at week n = week n – baseline, n=24
- Proportion of subjects with change ≤ 0 = the number of subjects with change ≤ 0 / the number of subjects with non-missing values x 100

9.2.11.2 Method of Analysis

Refer to section 9.2.9.2.

9.3 Exploratory Evaluation Endpoint(s)

- 1) Change from the baseline in total tau (t-tau), phosphorylated tau (p-tau), and neurofilament light chain (NfL) markers in blood after 12 weeks (3 months), and in blood and cerebrospinal fluid after 24 weeks (6 months) of investigational product administration
- 2) Change from the baseline in inflammatory cytokine markers (IL-6, IL-8, IL-2, IFN- γ , TNF- α , etc.) in blood after 12 weeks (3 months), and in blood and cerebrospinal fluid after 24 weeks (6 months) of investigational product administration
- 3) Change from the baseline in blood after 12 weeks (3 months), and in blood and cerebrospinal fluid markers after 24 weeks (6 months) of investigational product administration, and correlation between clinical markers and treatment responses

9.3.1 Change from the baseline in total tau (t-tau), phosphorylated tau (p-tau), and neurofilament light chain (NfL) markers in blood after 12 weeks (3 months), and in blood and cerebrospinal fluid after 24 weeks (6 months) of investigational product administration

9.3.1.1 Variable, Definition and/or Derivation

- pTau181, pTau217, pTau231, Total tau, NfL
- Change from baseline at week n = week n – baseline, n=12, 24

9.3.1.2 Method of Analysis

Refer to section 9.2.2.2.

9.3.2 Change from the baseline in inflammatory cytokine markers (IL-6, IL-8, IL-2, IFN- γ , TNF- α , etc.) in blood after 12 weeks (3 months), and in blood and cerebrospinal fluid after 24 weeks (6 months) of investigational product administration

9.3.2.1 Variable, Definition and/or Derivation

- IL-6, IL-8, IL-2, IFN- γ , TNF- α , GFAP, UCH-L1
- Change from baseline at week n = week n – baseline, n=12, 24

9.3.2.2 Method of Analysis

Refer to section 9.2.2.2.

9.3.3 Change from the baseline in blood after 12 weeks (3 months), and in blood and cerebrospinal fluid markers after 24 weeks (6 months) of

investigational product administration, and correlation between clinical markers and treatment responses

9.3.3.1 Variable, Definition and/or Derivation

- pTau181, Total tau, NfL, IL-6, IL-8, IL-2, IFN- γ , TNF- α , GFAP, UCH-L1
- Change from baseline at week n = week n – baseline, n=12, 24

9.3.3.2 Method of Analysis

To determine the association of each biomarker with each treatment response, a correlation coefficient is calculated for the 12 weeks and 24 weeks change from baseline for each treatment group. The correlation coefficient is calculated using Pearson's correlation coefficient or Spearman's correlation coefficient, depending on the normality of the data.

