3.1.2 Secondary Objective

To collect source data to determine the possibility of progression to the next stage of development and to subsequent clinical studies by analyzing the clinical and biological parameters associated with the treatment response and safety information of 2 dose levels of GV1001, 0.56 mg/day or 1.12 mg/day, in patients with progressive supranuclear palsy.

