3.2 Study Design

This is a 24-week, multicenter, randomized, double-blind, placebo-controlled, parallel design, prospective, Phase 2a exploratory clinical study.

If the subject and/or the subject's representative provide a written consent to participate in this clinical study, the required examinations and tests will be performed at the screening visit, and the screening period will run for 4 weeks or shorter.

Subjects who are ultimately determined as eligible by the inclusion/exclusion criteria after screening will be randomized at a 1:1:1 ratio to Study Group 1 (GV1001 0.56 mg/day), Study Group 2 (GV1001 1.12 mg/day), or the placebo group depending on the study site in which they are enrolled. Depending on the randomization results, subjects will be administered the investigational product (study drug or placebo) once weekly for the first 4 weeks (1 month), and then administered 10 times at 2-week intervals for 20 weeks (5 months) for a total of 14 doses over 24 weeks (6 months).

All subjects will visit the study site according to the planned clinical study schedule to receive the investigational product and to be evaluated for efficacy and safety. To ensure the objectivity and accuracy of the study results, the efficacy evaluators evaluating the PSP-rating scale will be limited to neurologists who have been sufficiently educated and trained, and the collection of efficacy and safety evaluation data and biomarkers will be performed in a consistent order at each visit.

※ Neurological drugs administered at a stable dose for at least 1 month prior to a subject's participation in this clinical study (prior to screening) will be continued without changing the dose during the clinical study participation period.

[figure not shown]

Figure. Clinical Study Schematic

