3.3 Determination of the Sample Size

Total number of subjects: 75 subjects (75 subjects in total with 25 subjects per group considering a dropout rate of 20%)

	Study Group 1	Study Group 2	Control Group	Total Number of Subjects
Number of Subjects	20	20	20	60
Number of Subjects Considering Dropout (20%)	25	25	25	75

This is a Phase 2a exploratory clinical study conducted for the purposes of collecting initial safety and efficacy information on the investigational product GV1001 in patients with progressive supranuclear palsy as well as providing the basis for design, evaluation items, and evaluation methods for subsequent clinical studies. Since this is a study to estimate the clinically significant effect size to demonstrate the efficacy of this investigational product, the number of subjects was not calculated based on statistical considerations. The minimum number of subjects required in a pilot study is 12 subjects²⁾ and approximately 30 subjects can be considered according to the rule of thumb^{3), 4)}. Therefore, by combining these, it is intended to set 20 subjects per group, and a total of 75 subjects with 25 subjects per group will be enrolled considering a dropout rate of 20%.

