5. GENERAL CONSIDERATIONS FOR SUMMARIES AND ANALYSES

5.1 Significance Level

Unless otherwise specified, all statistical tests will be two-sided hypothesis tests performed at the 5% level of significance and all confidence intervals will be two-sided 95% confidence intervals.

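### Biomarker–response correlations are planned only within arms of about 20, with a coefficient type that depends on a normality test and two p-tau forms left out, so they give weak support to the biomarker part of the secondary objective

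*SAP*

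**What the plan says.** The method in SAP 9.3.3.2 is short: "a correlation coefficient is calculated for the 12 weeks and 24 weeks change from baseline for each treatment group". The coefficient is Pearson's or Spearman's according to the normality of the data. SAP 5.2 makes normality a Shapiro-Wilk test at the 5% level. No estimate across arms, comparison between arms or adjustment for arm is described.

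The marker list in 9.3.3.1 starts "pTau181, Total tau, NfL, IL-6, IL-8, IL-2" and has ten markers in all. The list in 9.3.1.1, for the change-from-baseline analysis, is "pTau181, pTau217, pTau231, Total tau, NfL". So pTau217 and pTau231 are analysed for change but are not correlated with response. SAP 3.5, which records changes from the protocol, does not mention this. Neither 9.3.3.1 nor 9.3.3.2 says which clinical variables count as treatment response.

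On size, SAP 3.3 says "it is intended to set 20 subjects per group, and a total of 75 subjects with 25 subjects per group will be enrolled". Cerebrospinal fluid (CSF) is taken only from subjects who consent to it separately (SAP 3.4, note 6), so CSF numbers are unknown and may be smaller. SAP 12 and 13 plan no sensitivity or additional analyses.

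The secondary objective (SAP 3.1.2) includes "analyzing the clinical and biological parameters associated with the treatment response", as part of collecting data to decide on further development.

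**The concern.** The biomarker MMRMs in 9.3.1 and 9.3.2 compare each dose with placebo on each marker. They do not show whether a subject whose marker moves is also a subject whose clinical score moves. Only 9.3.3.2 asks that, and it divides the sample by three before asking.

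Three things follow. Each per-arm estimate is imprecise. If the type of coefficient differs between arms, a dose-to-dose comparison is partly a comparison of linear with monotonic association. And two of the three p-tau forms cannot be considered as response markers, although they are already being analysed. SAP 3.3 says the study should inform the evaluation items and methods of later studies; choosing markers for those studies is what this analysis would feed.

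**Working it through.** **Inputs.** From SAP 3.3: 20 evaluable and 25 enrolled per arm, 20% dropout. From SAP 3.2: 1:1:1 allocation. From SAP 5.1: "all statistical tests will be two-sided hypothesis tests performed at the 5% level of significance". My assumptions: an illustrative true correlation of 0.40, since the documents set no target; 12 CSF subjects per arm; the marker shapes in step 4.

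**1. The plan's own figure.** 20 / (1 - 0.20) = 25 per arm, and 3 × 25 = 75. It reproduces. The plan gives no precision or power for the correlations.

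**2. Precision.** The Fisher interval is tanh(atanh(r) ± 1.96 × SE). SE = 1/√(n - 3) within one arm, and 1/√(n - k - 3) for a partial correlation with k = 2 arm indicators. For r = 0.40, atanh(r) = 0.424.

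| Setting | SE | 95% interval |
|---|---|---|
| One arm, n = 20 | 1/√17 = 0.243 | -0.05 to 0.72 |
| All arms, n = 60, k = 2 | 1/√55 = 0.135 | 0.16 to 0.60 |
| CSF, one arm, n = 12 (assumed) | 1/√9 = 0.333 | -0.23 to 0.79 |
| CSF, all arms, n = 36, k = 2 | 1/√31 = 0.180 | 0.07 to 0.65 |

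The all-arm rows assume the same association within every arm. The formula is for Pearson; a Spearman interval is a little wider in every row.

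**3. Power.** Power is Φ(atanh(r)/SE - 1.96). For r = 0.40 it is Φ(0.424/0.243 - 1.96) = 42% in one arm and Φ(0.424/0.135 - 1.96) = 88% with all arms. The correlation detectable with 80% power is tanh(2.80 × SE): 0.59 in one arm, 0.36 with all arms.

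**4. Mixed coefficient types.** This step holds only if normality is tested separately in each arm and for each variable. If marker and response are both normal, the chance that at least one test rejects in an arm is q = 1 - 0.95² = 0.0975. The chance that the three arms do not all use the same coefficient is 1 - (1 - q)³ - q³ = 1 - 0.7351 - 0.0009 = 0.264, about 26%.

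For skewed markers I simulated log-normal values with 20 per arm, a baseline-to-follow-up correlation of 0.89 on the log scale, and a normal response. With log-SDs of 0.3, 0.5 and 0.8, the mixed-type rate was about 42%, 63% and 73% (4,000 runs each). If normality is instead judged once per variable over all arms, the rate is zero.

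**5. The p-tau lists.** SAP 9.3.1.1 has three p-tau forms; 9.3.3.1 has one. Protocol 10.3.17 describes one sample schedule for all exploratory markers: blood at Visits 1, 10 and 16, and CSF at Visits 1 and 16.

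**The case against.** The strongest reply is that this is an exploratory endpoint in a study that openly did not size itself statistically, so wide intervals are expected. The value 0.40 is mine. At a true correlation of 0.60, per-arm power is already about 82%. That stands, and it limits the point to modest associations.

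Within-arm estimation is also defensible in itself. It keeps the treatment effect out of the coefficient, and the association may differ between arms: placebo subjects have no response to drug, so their data show how a marker tracks natural progression. That stands too. It argues against replacing the per-arm values, but not against adding an adjusted estimate beside them.

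On switching, 9.3.3.2 does not say that normality is tested by arm. SAP 14.1 and 14.5, which might settle it, appear only as headings in the text I had, and the mock-up tables only as a title. The rates in step 4 are therefore conditional.

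A reader might infer that the correlations cannot answer the secondary objective. The documents do not support that. The objective is broad: it covers clinical and safety data, and the biomarker MMRMs, which include all three p-tau forms, also serve it. A reader might also call the shorter p-tau list an undeclared departure from the protocol. Protocol 10.4.3 names no markers for this endpoint, and 11.2.9 leaves the method open. What remains is an unexplained difference between two SAP lists.

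**Conclusion.** The point holds as a minor one. As specified, the correlations give only weak support to the biomarker part of the secondary objective. For r = 0.40 the all-arm interval is a little over half as wide as the per-arm one (0.44 against 0.77 on the correlation scale). That gain rests on 60 evaluable subjects and a similar association in each arm. The risk of coefficients that cannot be compared across arms is real only under arm-by-arm normality testing; the SAP should remove the ambiguity either way. The missing p-tau forms and the unnamed response variables can be seen in the text and need no assumption. None of this affects the primary analysis.

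**What to change.** In SAP 9.3.3.2:

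- Use Spearman throughout and drop the normality switch.
- Keep the per-arm coefficients. Add a partial Spearman correlation, adjusted for treatment arm, over all FAS subjects with both values. Give 95% intervals for both.
- Report blood at Weeks 12 and 24 and CSF at Week 24 separately.
- Name the response variables, including at least the change in PSP-rating scale total score.

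In SAP 9.3.3.1, add pTau217 and pTau231.

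The cost is SAP wording and table rows, with no new samples or visits. For each response variable, the per-arm table grows from 10 × 3 × 3 = 90 coefficients (markers, matrix-and-week combinations, arms) to 12 × 3 × 3 = 108, and the combined table adds 12 × 3 = 36. There are two drawbacks. The combined estimate assumes a similar association in each arm, which readers can check against the per-arm values. Spearman is slightly less efficient than Pearson if the data are normal.

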10. SAFETY ANALYSES

10.1 Extent of Exposure

10.1.1 Variable, Definition and/or Derivation

Variables	Definition and/or Derivation
Treatment Duration (days)	
Date of last IP administration – Date of first IP administration + (additional time exposed)*
 
*additional time exposed = 1, if the subject completes V15 = Minimum(6, Discontinuation date – Date of last administration) + 1, discontinued before V4 = Minimum(13, Discontinuation date – Date of last administration) + 1, discontinued after V4

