9.1. Administration and Treatment Schedule

For 24 weeks (6 months) according to the randomization results, this clinical study will administer GV1001 0.56 mg/day for Study Group 1, GV1001 1.12 mg/day for Study Group 2, and a placebo of GV1001 for the control group once weekly for the first 4 weeks (1 month), and thereafter 10 times at 2-week intervals for 20 weeks (5 months) for a total of 14 subcutaneous doses over 24 weeks (6 months).

See section 8.3 Dosage, Administration Method, and Administration Period for details.

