10.2.8. Visit 15 (End-of-Treatment Visit; Week 24 ± 5 days)

- Changes in the prior/concomitant drug administration history will be checked compared with the previous visit.
- A physical examination will be performed.
- Vital signs will be measured.
- The occurrence of adverse events after the administration of the investigational product at the previous visit and their details will be investigated.
- The investigational product will be administered after confirming that the clinical study can be continued.
- The subjects will be observed for adverse events for approximately 20 minutes after investigational product administration.
- The date of the next visit will be designated.

10.2.9. Visit 16 (Week 24 [6 months] Efficacy Evaluation, Week 26 ± 5 days)

At this visit, the Week 24 (6 months) efficacy evaluation will be performed.

- Changes in the prior/concomitant drug administration history will be checked compared with the previous visit.
- A physical examination will be performed.
- Vital signs will be measured.
- Weight will be measured.
- Electrocardiography will be performed.
- Laboratory tests will be performed.
- Urine hCG pregnancy tests will be performed only for women of childbearing potential, excluding subjects confirmed to have undergone surgical sterilization and as being menopausal.
- The PSP-rating scale test will be performed.
- The MoCA-K test will be performed.
- The K-FAB test will be performed.
- The ES ADL test will be performed.
- Human-derived samples (DNA, plasma, serum, cerebrospinal fluid) will be collected for exploratory evaluations. However, in the case of cerebrospinal fluid, it will be collected only from subjects who have separately consented to collection of samples.
- The occurrence of adverse events after the administration of the investigational product at the previous visit and their details will be investigated.
- The date of the next telephone visit will be scheduled.

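### SAP 10.1.1 counts treatment duration on one basis for completers and another for dropouts, and it lengthens the post-dose credit at V4 although weekly dosing runs through V5

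*SAP*

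**What the plan says.** SAP section 10.1.1 gives treatment duration in days as "Date of last IP administration – Date of first IP administration + (additional time exposed". The added time takes one of three values:

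- completers: "additional time exposed = 1, if the subject completes V15";
- early discontinuation: "Minimum(6, Discontinuation date – Date of last administration) + 1, discontinued before V4";
- later discontinuation: "Minimum(13, Discontinuation date – Date of last administration) + 1, discontinued after V4".

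SAP section 3.2 gives the dosing schedule as "once weekly for the first 4 weeks (1 month), and then administered 10 times at 2-week intervals for 20 weeks (5 months", and protocol section 9.1 agrees: "once weekly for the first 4 weeks (1 month), and thereafter 10 times at 2-week intervals". The visit table in SAP section 6.2 places the four weekly doses at V2 to V5 (Weeks 1 to 4) and the ten two-weekly doses at V6 to V15 (Weeks 6 to 24). Protocol section 10.2.8 is headed "Visit 15 (End-of-Treatment Visit; Week 24 ± 5 days", and a dose is given at that visit. Visit 16 (Week 26) carries the six-month efficacy evaluation and no dose. SAP section 10.1.2 summarises treatment duration descriptively, by group and in total, and lists it by subject.

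**The concern.** For dropouts the rule treats a dose as covering the interval that follows it, up to one dosing interval. For completers it stops the clock on the day of the last dose. No single definition of exposure gives both lines, and the SAP gives no reason for the difference. A table that mixes the two compresses the contrast between subjects who finish and subjects who leave late. If dropout differs between arms, the exposure table will understate that difference.

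The cap has a separate problem. A cap of 6 days suits a weekly gap and a cap of 13 suits a two-week gap, so the switch belongs after V5, the last weekly dose. The SAP places it at V4 and ties it to when the subject discontinued, not to which dose was the last one received.

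**Working it through.** **Inputs.** Week numbers and windows come from SAP section 6.2, the formula from SAP section 10.1.1, and the 24-week treatment period from protocol section 6.1.

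**Reproducing the schedule.** Nominal day = 1 + 7 × (week − 1). For V15 this is 1 + 7 × 23 = 162, and ±5 days gives 157 to 167, which matches the SAP window. The same rule gives:

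| Visit | V2 | V3 | V4 | V5 | V6 | V14 | V15 | V16 |
|---|---|---|---|---|---|---|---|---|
| Nominal day | 1 | 8 | 15 | 22 | 36 | 148 | 162 | 176 |

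The gaps after V2, V3 and V4 are 7 days. The first 14-day gap is V5 to V6.

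**Completers against late dropouts, SAP rule, on schedule.**
- Completer, 14 doses: (162 − 1) + 1 = 162 days.
- Last dose V14, 13 doses, discontinued 13 or more days later: (148 − 1) + 13 + 1 = 161 days.
- The same dropout with V14 at the end of its window (day 153): (153 − 1) + 14 = 166 days, more than the on-schedule completer.

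**One basis for both.**
- Interval convention (the dropout rule applied to completers up to Visit 16): 161 + 14 = 175 days on schedule, so 162 is 13 days short (13/175 = 7.4%). Within the windows, the V15 to V16 gap runs from 171 − 167 = 4 to 181 − 157 = 24 days. With the cap of 13, the shortfall is 4 to 13 days.
- First-to-last-dose convention (the completer rule applied to dropouts): completers stay at 162 and the V14 dropout has 147 + 1 = 148. The SAP figure of 161 is 13 days too many.

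**Effect on a group contrast (illustration).** Assume one arm has no dropouts and another loses 20%, all 13 or more days after V14. The 20% is borrowed from the dropout allowance in SAP section 3.3.
- SAP rule: 162.0 against 0.8 × 162 + 0.2 × 161 = 161.8; difference 0.2 days.
- Interval convention: 175.0 against 0.8 × 175 + 0.2 × 161 = 172.2; difference 2.8 days.
- First-to-last-dose convention: 162.0 against 0.8 × 162 + 0.2 × 148 = 159.2; difference 2.8 days.

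The two consistent conventions agree on the contrast. The SAP rule hides 2.6 days of it.

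**The V4 switch, judged by the interval convention.** Let d be the days from last dose to discontinuation, for a subject last dosed at V2, V3 or V4 who discontinues after V4. The excess is min(13, d) − min(6, d): 0 for d ≤ 6, 1 at d = 7, 4 at d = 10, and 7 for d ≥ 13. A subject last dosed at V4 with d ≥ 13 gets 14 + 14 = 28 days instead of 14 + 7 = 21.

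**Cases with no rule or two rules.** Discontinuation exactly at V4 falls under neither dropout line. A subject dosed at V15 who leaves before Visit 16 meets both the completer line (162 days on schedule) and the later-discontinuation line (up to 175).

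**The case against.** A reader might infer that the duration is wrong for nearly every completer. The documents do not support that. V15 is named the end-of-treatment visit and the last dose is given there. Last dose minus first dose plus 1 is a legitimate definition, and if treatment ends on the V15 dose date the dropout formula itself gives min(13, 0) + 1 = 1. Nothing in the SAP or protocol says that the days after the final dose count as exposure for completers. This objection stands, but it defends the completer line only. It does not explain why dropouts are credited with time that completers are not.

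A reader might also infer that early leavers as a class are miscounted by the V4 switch. They are not. On the interval convention, the rule is right for anyone who discontinues before V4 and for dropouts last dosed at V5 to V14.

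The consequences are also limited. Disposition is tabulated by group with reasons (SAP section 8.1), so late losses remain visible, and drug compliance is summarised separately (SAP section 8.7). Compliance does not fill the gap fully, because its denominator for dropouts stops at discontinuation. Adverse event incidence is per subject (SAP section 10.2.2.1), not per unit of exposure time, and the efficacy models do not use treatment duration.

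**Conclusion.** The point holds as an inconsistency of definition plus a misplaced cut-off. Completers and dropouts are counted on different bases. Either completers are 4 to 13 days short (13 on schedule), or dropouts are over-credited by up to 13 days; the documents do not settle which. In addition, subjects last dosed at V2 to V4 who discontinue after V4, and 7 or more days after that dose, are over-credited by up to 7 days against the SAP's own interval logic.

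The single figures assume visits on their nominal days, and the ranges use the SAP windows. The damage is confined to the descriptive exposure table and listing. Adverse event incidence and efficacy results are unaffected, so this is a minor correction, worth making before the derivation is programmed.

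**What to change.** State one convention in SAP section 10.1.1 and apply it to every subject. Either of these is consistent:

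- **(a)** last dose date − first dose date + 1 for everyone; or
- **(b)** a credit set by the last dose received: min(6, end date − last dose) + 1 if the last dose was at V2 to V4, and min(13, end date − last dose) + 1 if it was at V5 to V15. The end date is the discontinuation date, or the Visit 16 date for completers.

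Both remove the V4 problem, cover discontinuation exactly at V4, and give one answer for a subject dosed at V15 who leaves before Visit 16.

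The cost is one SAP table cell and one derivation line; no visit, dose or data collection changes. Option (a) leaves completers at 162 days on schedule and drops the post-dose interval for dropouts. Option (b) has a small downside: an on-schedule completer shows 175 days, which is 7 more than the stated treatment period of 24 × 7 = 168 days. A table footnote should say so.
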